6. Subject reports at least moderate pain over the last week, as assessed by PGI-S at Visit 1.
7. Subject agrees to use only acetaminophen treatment as needed for breakthrough pain related to fibromyalgia.

8. Subject agrees not to initiate or change any non-pharmacologic interventions (including normal daily exercise routines, chiropractic care, physical therapy, psychotherapy, and massage therapy) during the study. Any ongoing non-pharmacologic intervention must be stable for at least 30 days prior to screening.
9. Subject has a body mass index (BMI) $\leq 40 \text{ kg/m}^2$.
10. Subject's calculated creatinine clearance is $\geq 60 \text{ mL/minute}$ (Cockcroft-Gault formula).
11. Absence of impaired hepatic function characterized by a previous known diagnosis of chronic liver disease, and/or the presence of abnormal serum total bilirubin (TBL), or alanine transaminase (ALT), aspartate transaminase (AST), or alkaline phosphatase (ALP) $>1.5 \times$ upper limit of normal (ULN) at screening.
12. Except as noted in criteria 10 and 11, subject's clinical laboratory values are within normal limits or deemed not clinically significant by the Investigator.
13. Female subjects of child bearing potential with a negative pregnancy test prior to entry into the study and who are practicing a highly effective method of birth control (e.g., oral or parenteral contraceptives, intrauterine device, barrier [condom and spermicide], abstinence) and who do not plan to become pregnant, breastfeed, or donate ova during the course of the study and for 28 days after the final administration of investigational product.
14. Male subjects should use a highly effective method of birth control and refrain from sexual activity with female sexual partners who do not use a highly effective method of birth control during the study. Male subjects who are not surgically sterilized for at least 90 days prior to screening and sexually active with female partner(s), must agree to use barrier contraception (condom with spermicide) during the study. Subjects must agree to refrain from sperm donation during the study and for 90 days after the final administration of investigational product.

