11. Absence of impaired hepatic function characterized by a previous known diagnosis of chronic liver disease, and/or the presence of abnormal serum total bilirubin (TBL), or alanine transaminase (ALT), aspartate transaminase (AST), or alkaline phosphatase (ALP) >1.5 x upper limit of normal (ULN) at screening.

12. Except as noted in criteria 10 and 11, subject's clinical laboratory values are within normal limits or deemed not clinically significant by the Investigator.
13. Female subjects of child bearing potential with a negative pregnancy test prior to entry into the study and who are practicing a highly effective method of birth control (e.g., oral or parenteral contraceptives, intrauterine device, barrier [condom and spermicide], abstinence) and who do not plan to become pregnant, breastfeed, or donate ova during the course of the study and for 28 days after the final administration of investigational product.
14. Male subjects should use a highly effective method of birth control and refrain from sexual activity with female sexual partners who do not use a highly effective method of birth control during the study. Male subjects who are not surgically sterilized for at least 90 days prior to screening and sexually active with female partner(s), must agree to use barrier contraception (condom with spermicide) during the study. Subjects must agree to refrain from sperm donation during the study and for 90 days after the final administration of investigational product.
15. Subject has not participated in an interventional study for at least 30 days or has not taken investigational study medication for a period of at least 5 half-lives of the study medication, whichever is longer. Agrees not to participate in another interventional study while on treatment. Eligibility will be reviewed during the study via sponsor participation in a research subject database.
16. Subject has the ability to understand the requirements of the study, abide by the study restrictions, as well as concomitant medications exclusions and agrees to return for the required assessments.

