7.5. Methods of Birth Control

If heterosexually active and of childbearing potential, female subjects must agree to consistently use a highly effective method of birth control starting at Visit 1, continuing throughout the study, and for 28 days after the last dose of study drug. Methods of highly effective birth control include:

- Oral or parenteral contraceptives
- Intrauterine device (either hormonal or nonhormonal type acceptable)
- Barrier
- Abstinence

Female subjects must agree not to plan to become pregnant or breastfeed starting at Visit 1, during the study and for 28 days after the last dose of study drug. Female subjects must refrain

from donating ova during the study period and for 28 days after final administration of investigational product.

Male subjects must use a highly effective method of birth control and refrain from sexual activity with female sexual partners who do not use a highly effective method of birth control starting at Visit 1 through the last dose of study drug. Male subjects who are not surgically sterilized for ≥ 90 days prior to Visit 1 and are sexually active with a female partner must use a condom with spermicide during the study. Male subjects must refrain from sperm donation during the study and for 90 days after the final administration of investigational product.

All pregnancies (female subjects and female partners of male subjects) occurring during the study must be followed for information regarding the course of pregnancy, delivery, and condition of the newborn. Follow-up should be provided by the investigator to the Sponsor-designated Medical Monitor in a timely manner. When the newborn is healthy, further follow-up is not necessary.

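### Men may not donate sperm for 90 days after the last dose, but no male contraception period is counted from the last dose, and the male clauses end at different points

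*Protocol*

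**What the plan says.** The male rules stand in three places in the protocol.

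- **Criterion 14, Synopsis.** "condom with spermicide) during the study. Subjects must agree to refrain from sperm donation during the study and for 90 days" after the final administration.
- **Criterion 14, Section 7.1.** The general clause reads "Male subjects should use a highly effective method of birth control and refrain from sexual activity with female sexual partners who do not use" such a method, and applies during the study. Men who have not been surgically sterilised for at least 90 days before screening and are sexually active with a female partner "must agree to use barrier contraception (condom with spermicide) during the study". The 90-day donation ban is repeated.
- **Section 7.5.** The general clause becomes "Male subjects must use a highly effective method of birth control and refrain from sexual activity with female sexual partners who do not use" such a method, and its end point changes: it covers partners "who do not use a highly effective method of birth control starting at Visit 1 through the last dose of study drug". Men in the unsterilised group who are "sexually active with a female partner must use a condom with spermicide during the study". On donation: "Male subjects must refrain from sperm donation during the study and for 90 days after the final administration of investigational product".

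For women, Section 7.5 counts contraception from the last dose: "continuing throughout the study, and for 28 days after the last dose of study drug". The ban on donating ova has the same 28-day tail.

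The protocol does not say when the study ends for an individual subject. Section 6.1 describes 13 to 16 weeks, which is screening plus 12 weeks of treatment. Table 3, footnote y, schedules a call 7 to 10 days after Visit 6 and a final call 30 ± 5 days after Visit 6. Section 13.10 deals with administrative completion, not with when a subject's obligations stop.

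**The concern.** A man who follows the protocol text exactly may conceive by intercourse while he is still barred from donating sperm. The two precautions concern the same possible exposure route, and the protocol gives them different lengths without saying why. The female rules do not have this feature.

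The wording also shows that the donation period is meant to be longer than the study. Donation is barred during the study and then for a further 90 days, so *during the study* cannot be read to include those 90 days. The condom rule has only the first part.

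There is a second, smaller defect. The birth-control and partner clause has one end point in criterion 14 and another in Section 7.5, so a site cannot tell from the protocol which applies. What is at stake is the completeness and clarity of a participant-protection rule, not the interpretation of the trial.

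**Working it through.** **Inputs**

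- Donation ban: 90 days after the last dose (criterion 14; Section 7.5).
- Male condoms: during the study (all three places).
- Male birth-control and partner clause: during the study (criterion 14) or to the last dose (Section 7.5).
- Final safety call: 30 ± 5 days after Visit 6, so day 25 to day 35 (Table 3, footnote y).
- Female contraception and ova-donation ban: both 28 days after the last dose (Section 7.5).

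**Formula**

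Uncovered days = 90 − (days from last dose to Visit 6) − (days from Visit 6 to the end of the rule).

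**Last dose on the day of Visit 6**

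| End of the study taken as | Calculation | Uncovered days |
|---|---|---|
| Week 12 / Visit 6 | 90 − 0 − 0 | 90 |
| First safety call, day 7 to 10 | 90 − 10 to 90 − 7 | 80 to 83 |
| Final call, day 25 to 35 | 90 − 35 to 90 − 25 | 55 to 65 |

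**Last dose before the final visit** (lags are assumptions; 7 and 14 days stand for a delayed early-termination visit)

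| Lag | Study ends at final visit | Study ends at final call |
|---|---|---|
| 1 day | 90 − 1 = 89 | 90 − 1 − 35 = 54 to 90 − 1 − 25 = 64 |
| 7 days | 90 − 7 = 83 | 90 − 7 − 35 = 48 to 90 − 7 − 25 = 58 |
| 14 days | 90 − 14 = 76 | 90 − 14 − 35 = 41 to 90 − 14 − 25 = 51 |

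The gap shrinks with a longer lag but stays open throughout.

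**Section 7.5 taken clause by clause.** The birth-control and partner clause stops at the last dose, which leaves 90 − 0 = 90 days for that clause alone. The condom rule in the same section still runs during the study, so for unsterilised men with a female partner the uncovered period is again 55 to 65 days if the study ends at the final call.

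**Comparison with women.** 28 − 28 = 0 days between the end of contraception and the end of the ova-donation ban.

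**Men affected.** The protocol gives no expected sex split. The Introduction cites a 7:1 female-to-male ratio for diagnosis; applying it to enrolment is an assumption. Men: 300 / 8 = 37.5. In the two active arms, with 100 per arm (SAP Section 4): 37.5 × 2/3 = 25. If 5% to 20% of subjects were men: 300 × 0.05 = 15 to 300 × 0.20 = 60, of whom 10 to 40 would be on NYX-2925. The share who are unsterilised and sexually active is not given, so these are upper limits on the number concerned.

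**The case against.** The best defence is that a donation ban and contraception are separate precautions that need not have the same length. Nothing in the documents ties the 90 days to a paternal risk period, so the ban may be generous and the contraception period adequate. The Introduction reports peak concentrations within two hours, decline over 24 hours, minimal accumulation over seven days, and dog exposure at the no-adverse-effect level about 70-fold and 20-fold that at 50 mg and 150 mg. That makes a short male period plausible, and this part of the defence stands. It is why a shorter stated period would be an acceptable answer. It does not remove the point: these are general data, no reproductive toxicology is reported, and the text neither explains the 90 days nor says the difference is intended.

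Several stronger readings are tempting and should not be drawn.

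- A reader might infer a demonstrated hazard to partners or offspring. The documents show none.
- A reader might take Section 7.5 as a fixed 90-day gap for every man. Its condom rule, which covers the men who could conceive, may run on to the final call.
- A reader might treat 55 days as a floor. It assumes the last dose is on the day of Visit 6; the table above shows lower figures.
- A reader might make much of should against must. Criterion 14 sits in a list that subjects must meet in full, and its condom and donation sentences already say must. The difference is untidy, not a loophole.
- A reader might infer that subjects receive no further instruction. The consent pages are not in the copy reviewed, so only the protocol text can be judged.
- A reader might cite pregnancy follow-up, which is limited to the study period, as part of the same fault. That limit applies to both sexes and does not show a male-specific mismatch.

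**Conclusion.** The inconsistency is real and stands in the current text of the Synopsis, Section 7.1 and Section 7.5; nothing else in the protocol or SAP closes it. Its size depends on two things the protocol leaves open: when the study ends for a subject, and how close the last dose is to the final visit. With the last dose at Visit 6, roughly 55 to 65 days are uncovered on the final-call reading and about 90 on the Week 12 reading. The 13- to 16-week description favours the second reading, but the scheduled calls prevent certainty.

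The consequence is an incomplete and unclear precaution for a small number of men, with no paternal hazard shown. The point is low priority. It has no bearing on the endpoints, the power or the type I error rate.

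**What to change.** In criterion 14 (Synopsis and Section 7.1) and in Section 7.5, state that male subjects must use the required contraception, including condoms where they apply, from Visit 1 through 90 days after the last dose. That matches the donation ban and gives every male clause one end point counted from dosing, so the undefined end of the study no longer matters. If the sponsor's reproductive toxicology supports a shorter period, state that period and its basis instead, again in identical words in all three places. No change to pregnancy reporting is needed for this point.

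The cost is wording in three places and the matching subject instruction, with no added visits or assessments. The downside is a longer contraception commitment for a small number of men.

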3. LIST OF ABBREVIATIONS AND DEFINITIONS OF TERMS

The following abbreviations and special terms are used in this study protocol.

Table 2: Abbreviations and Special Terms

Abbreviation	Explanation
ACR	American College of Rheumatology
AE	adverse event
ALP	alkaline phosphatase
ALT	alanine transaminase
ANCOVA	analysis of covariance
APR®	Accurate Pain Reporting®
AST	aspartate transaminase
BOLD	whole-brain blood oxygenation level dependent
CFR	Code of Federal Regulations
C _{max}	maximum plasma concentration
CRP	C-reactive protein
CSF	cerebrospinal fluid
DSIS	Daily Sleep Interference Scale
DSM-5™	Diagnostic and Statistical Manual of Mental Disorders – Fifth Edition
ECG(s)	Electrocardiogram(s)
eCRF	electronic case report form
fcMRI	functional connectivity magnetic resonance imaging
FDA	Food and Drug Administration
FIQR	Fibromyalgia Impact Questionnaire - Revised
Free T ₄	free thyroxine
GAD	generalized anxiety disorder
GCP	Good Clinical Practice
GLx	glutamate + glutamine metabolites
[REDACTED]	[REDACTED]
HIPAA	Health Insurance Portability and Accountability Act
HIV	human immunodeficiency virus
HMRS	proton magnetic resonance spectroscopy
ICA	independent component analysis
ICF	informed consent form

Abbreviation	Explanation
ICH	International Council for Harmonisation
IRB	Institutional Review Board
IRT	interactive response technology
MADDERS	Misuse, Abuse, and Diversion Drug Event Reporting System®
MDD	major depressive disorder
MDE	major depressive episode
MedDRA	Medical Dictionary for Regulatory Activities
MINI	Mini-International Neuropsychiatric Interview
MMRM	mixed model for repeated measures
NF	National Formulary
NMDA	N -methyl- D -aspartate
NMDAR	N -methyl-D-aspartate receptor
NRS	numeric rating scale
NSAID(s)	nonsteroidal anti-inflammatory drug(s)
NYHA	New York Heart Association
pDPN	painful diabetic peripheral neuropathy
PGI-C	Patient Global Impression of Change
PGI-S	Patient Global Impression of Severity
PROMIS _{FM}	Patient Reported Outcomes Measurement Information System – Fibromyalgia
PRR®	Placebo Response Reduction®
REM	rapid eye movement
RM	rescue medication
SAE	serious adverse event
S-STS	Sheehan Suicidality Tracking Scale
T ₃	Triiodothyronine
T ₄	Thyroxine
TBL	total bilirubin
TEAE	treatment-emergent adverse event
THC	tetrahydrocannabinol
TSH	thyroid stimulating hormone
VCT	Verified Clinical Trials
ULN	upper limit of normal

Abbreviation	Explanation
USP	United States Pharmacopeia

Note: Abbreviations that appear only in tables or figures are defined in the appropriate tables or figures.

4. INTRODUCTION

NYX-2925 is a novel small molecule being developed for the treatment of neuropathic pain and fibromyalgia. This molecule interacts with N-methyl-D-aspartate receptors (NMDARs) through a novel binding domain and acts as a co-agonist with glutamate. NYX-2925 appears to act at a binding site that is distinct from NMDAR agonists or antagonists studied to date, such as D-cycloserine, ketamine, MK-801, or kynurenic acid. The NYX-2925 mode of action is distinct from that of all existing and emerging drugs that are indicated for the treatment of neuropathic pain and fibromyalgia. While current medications target individual elements of pain signal transmission or modulation, NYX-2925 modulates multiple synaptic relays within pain circuits.

Glutamate is the major excitatory neurotransmitter in the central nervous system and acts through activation of glutamate receptors. A portion of the receptors bind preferentially to *N*-methyl-D-aspartate (NMDA), and are, therefore, termed NMDARs. Unlike other glutamate receptors found in the brain, such as α -amino-3-hydroxy-5-methyl-4-isoxazolepropionic acid or kainic acid receptors, the NMDARs are unique in that they have distinct binding sites for both glutamate and glycine, and binding by both ligands is required for receptor activation. The NMDARs are implicated in a number of physiological and pathological processes, including anxiety, cognition, learning, stroke, schizophrenia, Parkinson's disease, and neuropathic pain [Tai 2001; Mony 2009; Traynelis 2010].

Fibromyalgia is a chronic, debilitating, disorder typified by widespread musculoskeletal pain, accompanied by symptoms of fatigue, affected sleep, memory issues, and mood disorders. It is estimated that fibromyalgia affects 5 million people or 2 to 5% of the American adult population [Arnold 2012]. Women are more commonly diagnosed than men (female:male ratio is 7:1) and prevalence increases with age.

Individuals suffering from fibromyalgia presently have limited treatment options available. Current treatment options include pregabalin, a calcium channel alpha-2-delta subunit ligand, and two norepinephrine and serotonin reuptake inhibitors, duloxetine and milnacipran. These therapies have shown some efficacy in treating fibromyalgia symptoms, although for a large proportion of patients, treatment is insufficient.

Recent research suggests that the chronic widespread pain seen in fibromyalgia patients has a neurogenic origin. Higher levels of ascending pathway neurochemicals, including nerve growth factor, substance P, and brain-derived neurotrophic factor, are present in the cerebrospinal fluid (CSF) of fibromyalgia patients when compared to healthy controls. In addition, glutamate levels can be elevated in both the CSF and brain of fibromyalgia patients. Glutamate may play a central role by acting on NMDARs to increase the central amplification of pain perception, which is thought to manifest as allodynia and hyperalgesia in fibromyalgia patients [Clauw 2011]. NMDA receptors are thus an attractive target for fibromyalgia therapeutic drug development.

As in fibromyalgia, the central nervous system modulates the experience of pain in people with neuropathic pain, with the rostroventral medial medulla [Silva 2016], the dorsal anterior cingulate cortex [Russo 2015], the insula, and other brain regions [Ossipov 2010] all thought to be involved. Neuropathic pain is caused by disease or injury of the somatosensory system as opposed to nociceptive pain, where the sensory system is physiologically normal [Jensen 2014]. While neuropathic pain can initially arise within the central or the peripheral nervous system

through a wide range of etiologies, central nervous system modulation of the experience of pain is common, regardless of the specific precipitating factors or initial location of the pain.

Preclinical pharmacology studies support the study of NYX-2925 in both fibromyalgia and neuropathic pain, both of which are chronic pain syndromes involving central nervous system modulation of pain signals. NYX-2925 is effective in several models of neuropathic pain and has shown activity in the chronic unpredictable stress model of fibromyalgia. Animal models of neuropathic pain in which NYX-2925 was tested include the rat Bennett model of neuropathic pain, the rat streptozotocin model of diabetic peripheral neuropathy, and the rat Taxol® model of chemotherapy-induced neuropathic pain. Unlike gabapentin (150 mg/kg orally), NYX-2925 (1 to 30 mg/kg orally) produced a rapid and long-lasting analgesia in the rat Bennett model of neuropathic pain without changes in locomotor activity after a single dose. Further, in the chronic unpredictable stress model of fibromyalgia, NYX-2925 (10 mg/kg) has been shown to produce mechanical analgesia. In summary, these data support testing NYX-2925 in both fibromyalgia and neuropathic pain.

Pharmacokinetic studies in rats and dogs suggest that NYX-2925 is rapidly absorbed into the bloodstream, with time to peak plasma concentration being reached within one hour. NYX-2925 is rapidly eliminated from plasma, with an apparent terminal elimination half-life in the range of four to five hours in rats and one to two hours in dogs. Brain exposure is approximately 5% to 10% relative to plasma levels of NYX-2925 in rats.

Both single-dose and daily repeat-dose toxicology studies have been performed in rats and dogs. The maximum tolerated dose following a single oral exposure is at least 1000 mg/kg in both rats and dogs. After up to 13 weeks of daily oral administration in rats and dogs, the no-observed- effect level (NOEL) was the highest dose tested for rats (1000 mg/kg/day) and the no-observed- adverse-effect level (NOAEL) was 120 mg/kg/day in dogs. There were no adverse findings in rats. In a 42-day, repeat-dose dog study, minimal or mild changes were observed in liver parameters at the high dose of 180 mg/kg/day. Similar changes were observed in the 13-week, repeat-dose dog study at the high dose of 240 mg/kg/day: liver enzyme levels in plasma were increased, and microscopic examination of the liver revealed pigmented material within bile canaliculi and in the cytoplasm of hepatocytes. These changes in liver parameters were partially reversed after a two-week or four-week recovery phase. In the 13-week repeat-dose study in dog, these observations were considered adverse at 240 mg/kg/day; therefore, the NOAEL was 120 mg/kg in dog. Based on the data to date, the plasma levels (exposure) of NYX-2925 at the NOAEL of 120 mg/kg/day in dog, the most sensitive species, is considered to be approximately 70 and 20-fold the human dose of 50 mg and 150 mg, respectively.

As of June 2019, the clinical development program for NYX-2925 includes two completed Phase 1 studies in healthy volunteers, one ongoing, clinically complete Phase 1 study in healthy volunteers, one ongoing, clinically complete Phase 2 study in subjects with diabetic peripheral neuropathy (DPN), and one ongoing, clinically complete Phase 2 study in subjects with fibromyalgia. NYX-2925 exposure includes 154 healthy volunteers, 301 subjects with DPN, and 23 subjects with fibromyalgia.

In NYX-2925-1001, a Phase 1 single and multiple ascending dose safety and tolerability study in healthy volunteers, pharmacokinetic analysis revealed that absorption of NYX-2925 was relatively rapid; peak concentrations were achieved within two hours after dosing and declined in a roughly monophasic manner over 24 hours. The pharmacokinetic profiles were dose-

proportional over the dose range tested and showed minimal accumulation following once daily dosing for seven days. A high-fat, high-caloric meal decreased the rate of absorption and lowered peak plasma concentration by 10%, but had no impact on the extent of exposure, suggesting that the compound may be administered with or without food. The majority (approximately 60% to 70%) of the administered dose was eliminated as unchanged NYX-2925 in the urine. Central nervous system exposure was confirmed, and CSF concentrations increased proportionally as the dose increased.

NYX-2925-1003 was a Phase 1 randomized, double-blind, placebo-controlled, crossover study of the effects of NYX-2925 on sleep architecture in healthy male volunteers. Preliminary PD results from this study indicate that a single oral dose of 100 mg NYX-2925 in healthy subjects increased sleep efficiency (total sleep time) as well as non-rapid eye movement (NREM) sleep time without affecting rapid eye movement (REM) sleep or inducing daytime drowsiness in the placebo/NYX-2925 arm.

NYX-2925-1004 was a Phase 1 double-blind, randomized, sponsor-open, parallel, placebo-controlled exploratory study to assess the effect of multiple dose levels (10, 50, or 200 mg) of NYX-2925 on the brain function of healthy volunteers as measured by EEG and event-related potentials (ERPs). NYX 2925 was shown to acutely enhance NMDAR-dependent mismatch negativity (MMN) at the lowest dose tested (10 mg single dose) and quantitative electroencephalogram (EEG) changes along with auditory long-term plasticity changes were seen across the dose levels. This study also showed auditory long-term plasticity changes 3 and 7 days after a single dose.

In Phase 2 Study NYX-2925-2001, 301 subjects with neuropathic pain associated with DPN were evaluated for change in pain scores over the four-week treatment period comparing placebo to NYX-2925 (10, 50, or 200 mg). Overall, there were no significant differences between NYX-2925 and placebo with regard to the changes in pain scores over the four-week treatment period. A numerical improvement in change in average pain intensity compared with placebo was observed for NYX-2925 50 mg and 200 mg, especially in subjects not taking any concomitant analgesic medication. Sleep interference due to pain showed a trend toward improvement for NYX-2925 50 mg. A significant ($p < 0.01$) improvement from baseline in average daily pain intensity at Weeks 3 and 4 was observed for NYX-2925 50 mg compared to placebo in the post hoc analysis of subjects with ≥ 4 years of DPN.

A Phase 2 Study, NYX-2925-2002, was conducted in 22 women with a confirmed diagnosis of fibromyalgia. In a sequential manner, all subjects were to receive daily doses of placebo, 20 mg NYX-2925 and 200 mg NYX-2925 for two weeks each. At baseline and during each two-week treatment period, subjects underwent a series of functional magnetic resonance imaging (fMRI) scans, combined with proton magnetic resonance spectroscopy (^1H -MRS) to measure key brain activity markers known to be associated with central pain perception and processing. These were the primary outcome measures for this trial. Secondary endpoints included patient reported outcomes of average daily pain and worst daily pain measured using a numeric rating scale (NRS), the impact of fibromyalgia on the subjects' daily living measured by the revised Fibromyalgia Impact Questionnaire (FIQR) and Patient Reported Outcomes Measurement Information System – Fibromyalgia (PROMIS_{FM}). At Week 6, under the 200 mg treatment condition, preliminary analysis of the data suggest there were significant improvements with NYX-2925 compared to placebo using the above measures. Pharmacodynamic results from this

study revealed that NYX-2925 20 mg significantly reduced glutamate + glutamine (Glx) levels within the posterior insula, a region previously implicated in pain processing in fibromyalgia. Based on preliminary analyses, significant clinical improvements in exploratory endpoints were observed following treatment with NYX-2925 (week 6) compared to baseline (week 0) and placebo (week 2) were average daily pain (1.09-point reduction from baseline ($p=0.0027$) and 0.66-point reduction vs. placebo ($p=0.0072$)), worst daily pain score (0.98-point reduction from baseline ($p=0.0169$) and 0.61-point reduction vs. placebo ($p=0.0360$)), total FIQR score (9.6-point reduction from baseline ($p=0.0085$) and 6.3-point reduction vs. placebo ($p=0.0135$)) and PROMIS_{FM} Fatigue Profile total score: 5.4-point reduction from baseline ($p=0.0081$) and 5.6-point reduction vs. placebo ($p=0.0049$). Taken together, these results warrant further clinical investigation of NYX-2925 in fibromyalgia.

In addition, these data demonstrate that NYX-2925 has predictable PK, including penetration into the CSF and achieves PD effects as measured by changes in sleep and EEG in healthy volunteers and MRI and reported pain in subjects with fibromyalgia.

Overall, NYX-2925 has been safe and well tolerated at oral doses up to 200 mg daily for up to four weeks. Across the studies, there have been few severe treatment-emergent adverse events (TEAEs), serious adverse events (SAEs), or TEAEs leading to study discontinuation, and no deaths. The most commonly reported TEAEs have been headache, diarrhea, upper respiratory tract infection, alanine aminotransferase increased, and arthralgia. No subject reported a SAE while receiving NYX-2925. An NYX-2925-2001 related TEAE leading to study discontinuation (severe headache) was reported, which occurred for a subject receiving daily NYX-2925 10 mg in Study NYX-2925-2001. One NYX-2925-2002 subject had an unrelated TEAE of mild ventricular extrasystoles leading to study discontinuation with onset during the placebo period and was discontinued after 1 dose of NYX-2925 20 mg.

No clinically meaningful changes in vital sign measurements, safety 12-lead electrocardiogram (ECG) results, physical examination findings, Columbia-Suicide Severity Rating scale (C-SSRS), or Sheehan–Suicidality Tracking Scale (S-STS) scores have been observed after a single dose of NYX-2925. Few potentially clinically significant laboratory results were observed during four weeks of treatment in Study NYX-2925-2001; however, these were generally comparable across treatment groups. A single subject in the NYX-2925 10 mg group had elevated clinical laboratory results, including alanine aminotransferase increased and aspartate aminotransferase increased, that met investigative product stopping criteria. On the NYX-2925-2002 study, one (4.8%) subject had a potentially clinically significant GGT result in the NYX-2925 200 mg period and also experienced elevated ALT and AST. These elevations occurred during the NYX-2925 200 mg period and declined following the end of dosing; however, GGT remained above the laboratory reference range at last evaluation, though trending downward.

In summary, NYX-2925 has been sufficiently tested in preclinical studies for safety and tolerability over a wide dose range, with exposures greater than the proposed clinical doses. General toxicology studies in rats and dogs support clinical studies up to and including 13 weeks of daily doses. Clinical results to date indicate that NYX-2925 is safe and well tolerated. The preclinical, Phase 1 and preliminary Phase 2 clinical data support further testing for fibromyalgia in humans.

This study (NYX-2925-2005) is a randomized, double-blind, parallel-group, placebo-controlled study to assess the efficacy and safety of NYX-2925 in subjects with fibromyalgia. NYX-2925 will be provided as capsules for oral administration in strengths of 50 mg NYX-2925 or 100 mg NYX-2925 per capsule.

